### **8.6.2 Blood sample for RNA and DNA analyses and biomarker studies**

Immune-related features measured in blood samples may include immune-related messenger RNA expression signatures, blood TMB, and/or measurement of other analytes.

Additional translational research might be conducted as appropriate including but not limited to the assessment of T-cell clonality, neoantigen expression, metabolomics, proteomics, and presence and changes in the circulating tumor markers such as circulating tumor DNA at screening and following nanrilkefusp alfa and pembrolizumab treatment.

The correlation/relationship between biomarkers in tumor tissue and blood and measures of clinical efficacy, safety, PD activity, and/or mechanism of action will be evaluated.

For patients with mCRPC, CTC count and circulating tumor DNA will be analyzed.

Instructions on sample collection, handling, storage, and shipment of samples are detailed in the study-specific Laboratory Manual provided to the study site.

Samples may be stored for a maximum of 20 years (or according to local regulations) after the end of the study at a facility selected by the sponsor to enable further analysis of biomarker responses to nanrilkefusp alfa in combination with pembrolizumab.

### **8.7 Immunogenicity assessments**

Samples for ADAs will be collected to assess nanrilkefusp alfa tolerability, correlation with PK, and potential AEs associated with ADAs against nanrilkefusp alfa and for the prediction of nanrilkefusp alfa ADA production.

Samples for pembrolizumab ADAs will be collected. These samples will be stored and a decision about their analysis will be taken at a later date.

Instructions on sample collection, handling, storage, and shipment of samples is detailed in the study-specific Laboratory Manual provided to the study site.

Samples may be stored for a maximum of 20 years (or according to local regulations) after the end of the study at a facility selected by the sponsor to enable further analysis of immune responses to nanrilkefusp alfa in combination with pembrolizumab.

### **8.8 Health economics**

Health economics parameters will not be evaluated in this study.

### **8.9 Pharmacodynamics**

PD markers will be assessed in paired tumor tissue collected before and after treatment with nanrilkefusp alfa in combination with pembrolizumab. Activation/expansion of various immune cell populations (leukocytes including NK cells, CD8+ and CD4+ T cells, myeloid cells) will be detected based on the expression of specific markers by immunohistochemistry analysis or genetic analysis (optional).

## 9 STATISTICAL CONSIDERATIONS

### 9.1 Statistical hypotheses

No formal testing of statistical hypotheses is planned in this open-label, single-arm trial.

The primary objective is to estimate the antitumor efficacy of nanrilkefusp alfa in combination with pembrolizumab according to RECIST 1.1 by means of ORR, for each indication or disease cohort separately. Other efficacy endpoints (e.g., iORR, [i]PFS, [i]BOR) will also be explored to further evaluate the antitumor efficacy of the combination therapy.

### 9.2 Analysis sets

#### 9.2.1 All-subjects-as-treated population

The all-subjects-as-treated (ASaT) population will consist of all patients exposed to nanrilkefusp alfa or pembrolizumab.

All safety analyses will be performed on the ASaT population.

#### 9.2.2 PK population

The PK population will consist of all patients who are PK-evaluable. Please also see sections [1.3.5](#) and [8.4](#).

#### 9.2.3 Efficacy population

The efficacy population will consist of all patients exposed to the combination therapy for at least one treatment cycle.

This will be the main population for the analyses of the primary endpoint and efficacy, secondary, and exploratory endpoints.

#### 9.2.4 Per Protocol population

The per Protocol (PP) population is defined as all patients who had at least one full treatment cycle of nanrilkefusp alfa and pembrolizumab, did not violate any eligibility criteria, and did not have any major Protocol deviations.

### 9.3 Statistical analyses

#### 9.3.1 General considerations

Analyses will be descriptive (i.e., without a comparison). Efficacy analyses will be performed for each indication separately. Safety will be analyzed as described in section [9.3.3](#).

Summary statistics will include:

- Counts and percentages (categorical data)
- Number of observations, mean, standard deviation, median, minimum, and maximum (continuous data)

The ORR, iORR, BOR, iBOR, CBR, iCBR, CTC response, and PSA response will use the exact method based on the binomial distribution[56](#) to derive 95% confidence intervals (CIs).

---

Kaplan-Meier estimations and estimations of median (if reached) with log-log 95% CI, Q1 (25th percentile), and Q3 (75th percentile) will be used for time to confirmed PSA progression (mCRPC only), DoR, iDoR, PFS, iPFS, TtR, iTtR, and OS. In case of a confirmed response or disease progression, the date of the first tumor assessment or PSA evaluated as response or progression will be used for the time-to-event variables.

Depending on the amount of missing data, a sensitivity analysis will be performed for time-to-event endpoints. If such an analysis is planned, it will be described in the final Statistical Analysis Plan (SAP).

The last value of PSA, CTC count, CT scan, bone scan, or MRI on or up to 28 days before the date of the first study treatment will be used as the baseline value for each assessment. Only tumor assessments prior to or at the date of initiation of further-line therapy and using CT scan, bone scan, or MRI will be used for the evaluation of tumor response.

### **9.3.2 Primary endpoint analysis**

The ORR is defined as the proportion of patients with CR or partial response (PR). ORR will be analyzed and presented as a point estimate and a 95% CI for each indication separately. Patients with missing data will be considered as non-responders.

Sensitivity analyses will include the use of:

- ASaT and PP populations
- No imputation of missing data

### **9.3.3 Secondary endpoints analysis**

#### **9.3.3.1 Safety endpoints**

- TEAEs

A TEAE is defined as an AE that started or worsened at or after the start of study treatment.

TEAEs will be summarized with counts and percentages. These will be provided for the incidence of, but not limited to: any TEAE, any serious TEAE, any grade 3-5 TEAE, any drug-related TEAE, any serious and drug-related TEAE, any grade 3-5 and drug-related TEAE, temporarily discontinued due to a TEAE, permanently discontinued due to a TEAE, death. TEAE incidence frequencies by system organ class (SOC) and preferred term (PT) will also be provided.

- AESIs

AESIs will be summarized with counts and percentages by SOC and PT.

- Safety laboratory findings, vital signs, and ECG

Safety laboratory findings, vital signs measurements, and ECG data will be summarized accordingly (if categorical or continuous data). Laboratory results will be summarized using SI units as appropriate.

Further details on analyses to be performed by indication and overall will be specified in the final SAP.

### 9.3.3.2 Efficacy endpoints

- iORR

The iORR is defined as the proportion of patients with complete response (iCR) or partial response (iPR) and will be analyzed and presented as a point estimate and a 95% CI for each indication separately. Patients with missing data will be considered as non-responders.

- BOR and iBOR

The BOR and iBOR are defined as the best response from the start of study treatment until progression of disease or death and will be summarized with counts and percentages together with a 95% CI for each indication separately. Stable disease (SD, iSD) needs to last at least 6 weeks from the baseline scan; if not, at least one follow-up scan is required to declare stable disease.

- DoR and iDoR

The DoR and iDoR are defined as the time until progression of disease for patients with partial response (PR, iPR) or complete response (CR, iCR) and will be summarized using Kaplan-Meier estimates for each indication separately. Responders will be considered to have an ongoing response if they: i) have not progressed, and ii) have not started a new anti-cancer therapy, and iii) have not been lost to follow-up, and iv) are alive.

Patients with missing data will be censored/considered as having an event as specified below:

Situation	Date of progression or censoring	Outcome
No progression, no death. No start of new anti-cancer therapy.	Date of the last evaluable tumor assessment.	Censored
No progression, no death. Start of new anti-cancer therapy.	Date of the last tumor assessment with non-progression before the start of new anti-cancer therapy.	Censored
Progression or death after one missed adequate tumor assessment.	Date of progression or death, whichever is earliest (if both occur).	Progressed
Progression or death after more than one missed adequate tumor assessment.	Date of the last evaluable tumor assessment.	Censored

- CBR and iCBR

The CBR and iCBR are defined as the number of partial responses (PR, iPR), complete responses (CR, iCR), and stable diseases (SD, iSD) and will be analyzed and presented as a point estimate and a 95% CI for each indication separately. Stable disease (SD, iSD) needs to last at least 6 weeks from the baseline scan; if not, at least one follow-up scan is required to declare stable disease. Patients with missing data will be considered as non-responders.

- PFS and iPFS

PFS and iPFS are defined as the time from the first day of study treatment until the first date of radiological disease progression or death and will be summarized using Kaplan-Meier estimates for each indication separately.

Patients with missing data will be censored/considered as having an event as specified below:

Situation	Date of progression or censoring	Outcome
Incomplete or no baseline tumor assessment	Date of the first day of study treatment	Censored
Start of new anti-cancer therapy	Date of the last tumor assessment with non-progression before the start of new anti-cancer therapy	Censored
Death before the first disease progression assessment	Date of death	Progressed
Death between adequate tumor assessment visits	Date of death	Progressed
Progression or death after one missed adequate tumor assessment	Date of progression or death, whichever is earliest (if both occur)	Progressed
Progression or death after more than one missed adequate tumor assessment	Date of the last evaluable tumor assessment	Censored
No progression, no death	Date of the last evaluable tumor assessment	Censored

- TtR and iTtR

TtR and iTtR are defined as the time from the first day of study treatment until the first date of partial response (PR, iPR) or complete response (CR, iCR) and will be summarized using Kaplan-Meier estimates for each indication separately. Patients with missing data will be censored at the last assessment date, date of death, or date of the first day of study treatment (if incomplete or no baseline tumor assessments), whichever occurs latest.

- CTC count conversion from  $\geq 5$  to  $< 5$  cells per 7.5 mL of blood

The CTC response is defined as the proportion of patients with CTC count conversion from  $\geq 5$  to  $< 5$  cells per 7.5 mL of blood and will be analyzed and presented as a point estimate and a 95% CI for the mCRPC indication. Patients with missing data will be considered as non-responders.

- Confirmed PSA decline of  $\geq 50\%$

The PSA response is defined as the proportion of patients with a PSA decline of  $\geq 50\%$  and will be analyzed and presented as a point estimate and a 95% CI for the mCRPC indication.

Responses will need confirmation by a second consecutive value obtained 4 or more weeks after the first value indicated a response. Response will be evaluated 6 months post trial entry. Evaluable patients with no confirmed response as defined above will be classified as non-responders.

- Time to confirmed PSA progression

Time to confirmed PSA progression is defined as the time from the first day of study treatment to the date of PSA progression and will be summarized using Kaplan-Meier estimates for the mCRPC indication.

PSA progression is defined as the date when an increase of 25% or more and an absolute increase of 2 ng/mL or more from the nadir are documented. For patients who have a decline in PSA during treatment, PSA progression must be confirmed by a second value 3 or more weeks later increased with respect to the nadir PSA.

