10.13.12 Time to Confirmed PSA Progression

Time to confirmed PSA progression is defined as the time from the first day of study treatment to the date of PSA progression, where PSA progression is defined as the date when an increase of 25% or more and an absolute increase of 2 ng/mL or more from the nadir (or baseline, whichever is lowest) are documented.

For patients who have a decline in PSA during treatment, PSA progression must be confirmed by a second value 3 or more weeks later increased with respect to the nadir PSA (or baseline, whichever is lowest). The date of the first PSA progression will be used; in patients with an unconfirmed PSA progression, date of the first PSA progression will be used if followed by treatment discontinuation.

This endpoint applies to the mCRPC cohort only.

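### In patients with a PSA decline, any second value above the nadir confirms PSA progression, so a rise that falls back almost to the nadir still counts, dated at the rise

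*Protocol*

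**What the plan says.** Time to confirmed PSA progression is a secondary endpoint for the mCRPC cohort.

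- **First step (Protocol 9.3.3.2):** progression is the date when "an increase of 25% or more and an absolute increase of 2 ng/mL or more from the nadir are documented".
- **Confirmation (Protocol 9.3.3.2):** this applies only to patients whose PSA declines during treatment: "PSA progression must be confirmed by a second value 3 or more weeks later increased with respect to the nadir PSA". No size is given for the second increase.
- **SAP 10.13.12:** the same rule, with a small change to the reference ("increased with respect to the nadir PSA (or baseline, whichever is lowest"). The reference is still the minimum, and there is still no size.
- **Event date (Protocol 9.3.1):** once confirmed, "the date of the first tumor assessment or PSA evaluated as response or progression will be used for the time-to-event variables".
- **Contrast with PSA response (Protocol 9.3.3.2):** "Responses will need confirmation by a second consecutive value obtained 4 or more weeks after the first value indicated a response". The progression rule does not require the second value to be consecutive.
- **A separate route in the SAP:** "in patients with an unconfirmed PSA progression, date of the first PSA progression will be used if followed by treatment discontinuation". That concerns rises without a confirming value and is not the subject here.

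**The concern.** The two steps use very different bars. The first asks for a material rise. The second asks only that a later value exceed the lowest value seen, which every later value does unless it equals or sets a low. The second sample may therefore show that the rise did not persist and still be taken as confirming it, and the event is then backdated to the spike.

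The rule reaches only patients whose PSA fell, the group in which duration of PSA control is of most interest. A weak confirmation step there gives too many events, dated too early, under an endpoint name that tells the reader they were confirmed. SAP 6.1 drops the exploratory endpoints after recruitment stopped; this one is secondary and remains in the plan.

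**Working it through.** The documents state no event rate or false-confirmation rate for this endpoint, so there is no figure to reproduce.

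**Step 1. Worked example, no assumption about variability.** Take a nadir of 20 ng/mL. The first step needs max(1.25 × 20, 20 + 2) = max(25, 22) = 25 ng/mL. A value of 26 triggers (+30%, +6 ng/mL). A value of 20.1 three or more weeks later is 0.1/20 = 0.5% above the nadir. As written it confirms, and the event is dated at the 26. Under the same threshold it fails, because 20.1 < 25.

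**Step 2. Why a later value usually passes.** If PSA is truly flat with independent errors, a new value exceeds the minimum of k earlier values with probability k/(k+1): 2/3 = 67%, 3/4 = 75%, 4/5 = 80% for k = 2, 3, 4. This ignores the first step, so it is not a false-event rate. Once noise has produced a trigger, the nadir tends to be an unusually low reading, and the next value exceeds it more often still.

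**Step 3. Simulation with the first step applied.**

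Inputs from the documents:
- first step of 25% and 2 ng/mL;
- confirmation only after a decline;
- reference is the lowest value so far, including baseline;
- PSA every other 3-week cycle from cycle 4 (Protocol 1.3.3), so 2 × 3 = 6 weeks.

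Assumptions, not in the documents:
- true PSA 100 ng/mL at baseline, then a flat 50 ng/mL;
- independent log-normal error with log-SD 0.05 to 0.20;
- 4 or 8 on-treatment values, 6-weekly throughout (about 24 or 48 weeks);
- the value right after a trigger is the one used to confirm.

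Every confirmed progression here is false. Paired figures are as written / same threshold on the second value (400,000 patients per row).

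| log-SD | values | noise trigger | next value confirms the first trigger | patients wrongly counted |
|---|---|---|---|---|
| 0.05 | 4 | 0.2% | 98% / 5% | 0.2% / <0.1% |
| 0.05 | 8 | 1.4% | 98% / 5% | 1.4% / <0.1% |
| 0.10 | 4 | 14% | 88% / 26% | 12.5% / 3.7% |
| 0.10 | 8 | 51% | 89% / 26% | 47.6% / 17.1% |
| 0.20 | 4 | 45% | 79% / 46% | 35.7% / 20.9% |
| 0.20 | 8 | 92% | 81% / 48% | 86.2% / 64.1% |

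With a plateau of 10 ng/mL after a baseline of 20 the results are close (lowest same-threshold figure 4%; wrongly counted 47.6% against 17.0% at log-SD 0.10 with 8 values). The fourth column measures the confirmation step itself: as written it lets most noise triggers through at every noise level. The last column also depends on how often noise triggers at all. Because the written rule does not require a consecutive value, other later values could also confirm, so the as-written figures are, if anything, low.

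**The case against.** - **The first step is the main noise filter.** Fluctuations below 25% or below 2 ng/mL never start the process. This stands. A reader might infer that PSA noise in general is counted as confirmed progression. The documents do not support that: at log-SD 0.05 about 1% or fewer of stable patients are wrongly counted, and neither document gives PSA variability. The high figures belong to the noisier, longer scenarios.
- **Confirmation is not automatic.** A value at or below the nadir fails it, about 2% to 21% of the time after a noise trigger in these scenarios. This also stands.
- **The wording might mean a second value that again shows progression.** That is possible, but neither text says so, and a programmer following SAP 10.13.12 would code a value above the nadir. Either intention calls for the same clarification.
- **The rule covers only patients with a decline.** A reader might infer that the cohort's Kaplan-Meier median is biased downward. That is not shown. In a check mixing decliners (true rise starting at a median of 9 months) with non-decliners whose PSA doubles every 3 months from day 1, at log-SD 0.10, the cohort median was the same under both rules when decliners were 20% to 60% of patients. It moved by one 6-week visit at 80% and 100%. The documents do not give the share of decliners.
- **Little rests on the endpoint.** It is descriptive, in one cohort of 51 planned patients. The futility rule uses ORR only, and recruitment has stopped. This limits the weight of the point but does not make the rule right.

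**Conclusion.** The concern holds for the confirmation step. That a rise returning almost to the nadir is recorded as confirmed, and dated at the rise, follows from the wording alone. That the step filters little is robust across the assumed noise levels. How many stable decliners would be misclassified is not robust: it runs from about 1% or less to 86% across the scenarios, and rests on independent errors and an assumed log-SD. The direction among decliners is clear (too many events, too early). A change in the cohort median is not established. The definition should be corrected before the endpoint is reported; no primary or futility conclusion depends on it.

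**What to change.** As a statistical endpoint definition only, in SAP 10.13.12 and Protocol 9.3.3.2: for patients with a PSA decline, count progression as confirmed when the next consecutive PSA value obtained 3 or more weeks after the first qualifying rise is also at least 25% and at least 2 ng/mL above the nadir (or baseline, whichever is lowest), with that reference fixed at the first trigger. Keep the event date at the first qualifying value.

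Fixing the reference stops it moving between the two steps. Requiring the next consecutive value stops a transient spike from being confirmed by an unrelated rise much later.

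The cost is a sentence in each document and a small change to the derivation, with no new data and somewhat fewer confirmed events. The rule as written can be kept as a sensitivity analysis. The change does not remove all noise events (64% remain at log-SD 0.20 with 8 values), and it does not touch patients without a decline, for whom no confirmation is stated.

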#### **9.3.4 Exploratory endpoint analysis**

- OS

OS is defined as the time from the first day of study treatment until the date of death and will be summarized using Kaplan-Meier estimates for each indication separately. Patients with missing data will be censored at the last time known to be alive.

#### **9.3.5 Other analyses**

Other sensitivity, secondary, and exploratory analyses such as PK, immunogenicity, biomarker exploratory analyses, and circulating tumor DNA fraction (mCRPC only) will be described in the final SAP. The population PK analysis will be presented separately from the main Clinical Study Report.

### **9.4 Interim analysis**

An analysis for futility will be performed when the sample size is considered enough for such analysis and for each indication, as described below in this section. Efficacy data and outputs will also be a part of the Independent Data Monitoring Committee (IDMC) review.

During this period, patient recruitment may be paused if the sponsor deems it appropriate to wait for the results of the futility analysis before enrolling additional patients.

Assuming a desired ORR, the futility analysis will be based on a comparison against a minimal ORR considered as both statistically and clinically relevant improvement as compared to the benchmark ORR. An 80% CI using the exact method for the ORR (alpha = 0.2, alpha = 0.1 one-sided) will be used.

The analysis will be based on the efficacy population.

---

If, for a certain indication, the ORR is:

1. lower than the minimal ORR, and
2. the 80% CI for the ORR does not include the minimal ORR,

it will be concluded that the combination treatment is futile as compared to benchmark treatment and thus the indication will be discontinued. However, patients still on treatment in the indication can continue combination therapy if recommended by the IDMC.

The criteria for conclusion of futility, for each indication, are defined as follows:

- Indication 1 (NSCLC): Benchmark ORR = 15%; minimal ORR = 23%; desired ORR = 30.6%
  - N = 21 patients if the number of responses is less than 2 ( $r < 2$ )
- Indication 2 (MSI-H/dMMR colorectal cancer): Benchmark ORR = 44%; minimal ORR = 54.1%; desired ORR = 62.5%
  - N = 12 patients if the number of responses is less than 4 ( $r < 4$ )
- Indication 3 (cSCC): Benchmark ORR = 44%; minimal ORR = 54.1%; desired ORR = 62.5%
  - N = 12 patients if the number of responses is less than 4 ( $r < 4$ )
- Indication 4 (advanced hepatocellular carcinoma): Benchmark ORR = 17%; minimal ORR = 25.3%; desired ORR = 33% (not applicable in France)
  - N = 19 patients if the number of responses is less than 2 ( $r < 2$ )
- Indication 5 (mCRPC): Benchmark ORR = 5%; minimal ORR = 10.4%; desired ORR = 16.4%
  - N = 35 patients if the number of responses is less than 1 ( $r < 1$ )
- Indication 6 (recurrent ovarian cancer): Benchmark ORR = 15%; minimal ORR = 23%; desired ORR = 30.6%
  - N = 21 patients if the number of responses is less than 2 ( $r < 2$ )

Additionally, the ORR will be evaluated on an ongoing basis (without stopping of recruitment). Other efficacy endpoints will be used as supportive information.

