### **10.1.11 Independent Data Monitoring Committee**

An IDMC will be established for this study to safeguard the interest and safety of the patients participating in the study and provide independent review and assessment of the efficacy and safety data in a systematic manner. In addition, the IDMC will review safety data from the first 10-12 patients across all indications.

The efficacy results will be presented via descriptive statistics during systematic reviews, no testing is planned.

The IDMC will be tasked with making a recommendation to the sponsor to continue, modify, or stop recruitment or the trial based on their assessment of efficacy and safety information. The membership, key responsibilities of the IDMC, and corresponding procedures will be defined in the IDMC charter.

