6.1 Changes from Protocol

The following changes to the protocol have been applied:

Endpoint of “Circulating tumor cell (CTC) count conversion from >5 to <5 cells per 7.5 mL of blood” for metastatic castration-resistant prostate cancer (mCRPC) only will be analyzed as a conversion from ≥ 5 to <5 cells per 7.5 mL of blood.

Endpoint of “Confirmed PSA decline of $\geq 50\%$ ” will not only evaluate the response at 6 months post-trial entry: all timepoints will be considered as per the schedule of assessments (Section 1.3.3 of Study Protocol).

Additional sensitivity analyses and exploratory endpoints:

As a sensitivity analysis for Best Overall Response (BOR) as per RECIST 1.1: BOR will also be performed as per Prostate Cancer Clinical Trials Working Group 3 (PCWG3)-modified RECIST 1.1 to study the effect of progressive disease in bone on the BOR, for patients with mCRPC.

As a sensitivity analysis to Clinical Benefit Rate (CBR) as per RECIST 1.1: CBR will also be performed for all patients in mCRPC – with both measurable and non-measurable disease – as per PCWG3-modified RECIST 1.1, to study the effect of progressive disease in bone on the CBR.

Other sensitivity analyses using All Subjects as Treated (ASaT) population on selected efficacy endpoints.

As per the EMA guideline on the evaluation of anticancer medicinal products in man, the endpoint PFS2 has been added as an exploratory endpoint.

Following Futility Analysis in August 2023, recruitment to the study was stopped. Exploratory Endpoints will no longer be analyzed.

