11.0 Interim Analyses

An analysis for futility will be performed when the sample size is considered enough for such analysis and for each indication, as described below in this section (for further details please refer to study protocol). Efficacy data and outputs will also be a part of the IDMC review.

The criteria for conclusion of futility, for each indication, are as follows:

- Indication 1 (Advanced and/or metastatic non-small cell lung cancer [NSCLC]):
 - N = 21 patients if the number of responses is less than 2 ($r < 2$)
- Indication 2 (Microsatellite instability-high [MSI-H] or mismatch repair deficient [dMMR] colorectal cancer):
 - N = 12 patients if the number of responses is less than 4 ($r < 4$)
- Indication 3 (Recurrent or metastatic cutaneous squamous cell carcinoma [cSCC]):
 - N = 12 patients if the number of responses is less than 4 ($r < 4$)
- Indication 4 (Advanced hepatocellular carcinoma):
 - N = 19 patients if the number of responses is less than 2 ($r < 2$)
- Indication 5 (Metastatic castration-resistant prostate cancer [mCRPC]):
 - N = 35 patients if the number of responses is less than 1 ($r < 1$)
- Indication 6 (Recurrent ovarian cancer):
 - N = 21 patients if the number of responses is less than 2 ($r < 2$)

For the purposes of interim analyses, in the case of ongoing patients with any unconfirmed response and for whom a confirmatory scan is still pending:

- Responders (PR, CR) or patients with SD that, at the time of the futility analysis, did not yet have a second (confirmatory) tumor assessment performed will be considered to have an Unconfirmed response (PR, CR) or Unconfirmed SD as BOR, respectively. Such BORs will be presented with "Unconfirmed" label.
- ORR will also include Unconfirmed PR and Unconfirmed CR in the numerator.

For the purpose of conducting the interim analysis, a temporary futility analysis population will be defined based on the patients which are deemed necessary for such interim analysis as described above. This population flag will be removed once all futility analyses have been performed.

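### Does the futility rule declare a cohort futile against benchmark when it tests only the minimal ORR?

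*Protocol*

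**What the plan says.** Protocol 9.4 (repeated in the synopsis) sets out the basis of the rule first: "the futility analysis will be based on a comparison against a minimal ORR considered as both statistically and clinically relevant improvement" over the benchmark ORR. An indication stops if its ORR is below the minimal ORR and "the 80% CI for the ORR does not include the minimal ORR". In that case "it will be concluded that the combination treatment is futile as compared to benchmark treatment", and the indication is discontinued. The section lists benchmark, minimal and desired ORRs for each cohort with a fixed look, for example "N = 21 patients if the number of responses is less than 2" for NSCLC and ovarian cancer.

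SAP 11.0 repeats the looks and counts (for mCRPC, "N = 35 patients if the number of responses is less than 1") and refers to the protocol for the rest. It does not use the benchmark phrase. For patients whose confirmatory scan is pending at the look, "ORR will also include Unconfirmed PR and Unconfirmed CR in the numerator". SAP 6.1 records the outcome: "Following Futility Analysis in August 2023, recruitment to the study was stopped". Under Protocol 10.1.11 the IDMC may recommend to "continue, modify, or stop recruitment or the trial based on their assessment of efficacy and safety information".

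**The concern.** The test and the conclusion appear to refer to different quantities. Both conditions use the minimal ORR, while the conclusion names benchmark treatment. If the interval that triggers the stop still contains the benchmark ORR, the data have not ruled out a response rate at or somewhat above benchmark. A literal reader could then take a stopped cohort to have been shown no better, or even worse, than benchmark.

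There is a second worry in the other direction. A futility look might be expected to stop most cohorts with no gain over benchmark, but this one lets most of them through. If a pass were read as a sign of benefit, that would be unfounded. Neither document gives the probability of stopping, so a reader cannot judge this without calculating it. Because recruitment has already ended after a futility analysis, the remaining stake is how stops and passes are described in the study report.

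**Working it through.** **Inputs (Protocol 9.4).** Benchmark / minimal / desired ORR, and the look:

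- NSCLC and ovarian: 15 / 23 / 30.6%; N = 21, stop if 1 or fewer responses
- CRC and cSCC: 44 / 54.1 / 62.5%; N = 12, stop if 3 or fewer
- HCC: 17 / 25.3 / 33%; N = 19, stop if 1 or fewer
- mCRPC: 5 / 10.4 / 16.4%; N = 35, stop if 0

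**Step 1: reproduce the boundaries.** For x responses in n, the 80% Clopper-Pearson limits are the 10th percentile of Beta(x, n−x+1) and the 90th percentile of Beta(x+1, n−x). With x = 0 the lower limit is 0 and the upper limit is 1 − 0.1^(1/n). For mCRPC, 1 − 0.1^(1/35) = 6.4%.

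| Cohort | Largest stopping count, 80% CI | Next count, upper limit | Minimal ORR |
|---|---|---|---|
| NSCLC, ovarian | 1/21: 0.5–17.3% | 2/21: 23.4% | 23% |
| CRC, cSCC | 3/12: 9.6–47.5% | 4/12: 55.9% | 54.1% |
| HCC | 1/19: 0.6–19.0% | 2/19: 25.7% | 25.3% |
| mCRPC | 0/35: 0–6.4% | 1/35: 10.7% | 10.4% |

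In every row the first interval excludes the minimal ORR and the next count does not. All six stated boundaries are therefore right.

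**Step 2: compare the same intervals with the benchmark.** At the largest stopping count each interval contains the benchmark (15, 44, 17 and 5%). One response fewer gives upper limits of 10.4% for 0/21, 38.6% for 2/12 and 11.4% for 0/19, all below benchmark. mCRPC has no lower count. So the overlap is a feature of the boundary count, not of every stop.

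**Step 3: probability of stopping.** P(stop) = P(X ≤ r−1) with X binomial(N, p). At benchmark:

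- NSCLC, ovarian: 0.85^21 + 21 × 0.15 × 0.85^20 = 0.0330 + 0.1221 = 15.5%
- HCC: 0.83^19 + 19 × 0.17 × 0.83^18 = 0.0290 + 0.1129 = 14.2%
- mCRPC: 0.95^35 = 16.6%

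| Cohort | Benchmark | Minimal | Desired |
|---|---|---|---|
| NSCLC, ovarian | 15.5% | 3.0% | 0.5% |
| CRC, cSCC | 15.0% | 4.1% | 0.9% |
| HCC | 14.2% | 2.9% | 0.5% |
| mCRPC | 16.6% | 2.1% | 0.2% |

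A cohort at benchmark passes 83% to 86% of the time. The ratio of pass probabilities, minimal to benchmark, is (1 − 0.0301)/(1 − 0.1550) = 1.15 for NSCLC and ovarian, 1.13 for CRC, cSCC and HCC, and 1.17 for mCRPC. A pass therefore says very little.

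**Step 4: read the conclusion in its place.** In Protocol 9.4 the paragraph before the conclusion defines the minimal ORR as a relevant improvement relative to benchmark. Both conditions then name the minimal ORR, and only after that comes the sentence about benchmark treatment. In that order, being futile relative to benchmark means that the improvement just defined is unlikely to be reached. An interval such as 0.5–17.3%, which excludes 23% and contains 15%, supports exactly that statement.

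**The case for a change.** The strongest case for a change is that one sentence has to hold for every count that triggers it, and the boundary counts are the usual ones. Among stops in a cohort truly at benchmark, the boundary count accounts for 0.1221/0.1550 = 79% in NSCLC and ovarian, 80% in HCC, 68% in CRC and cSCC, and all of them in mCRPC. The lower counts that exclude benchmark are the minority. The 14.2% to 16.6% figures may also be upper figures. If the benchmarks are confirmed response rates, counting unconfirmed responses makes stopping rarer. Assuming 80% to 95% of responses are later confirmed (a range not in the documents), and in the extreme case that every response at the look is unconfirmed, P(stop) at benchmark falls to 7–13% (NSCLC, ovarian), 4–12% (CRC, cSCC), 7–12% (HCC) and 10–15% (mCRPC). Finally, the rule acts by indication, whereas SAP 6.1 records a stop for the whole study without saying which cohorts met it.

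The arithmetic stands. It shows that the sentence could be worded more tightly and that a table of stopping probabilities would help a reader. It does not show a defect in the rule. Low stopping probabilities are the price of rarely discarding a cohort at the minimal ORR, and other looks would only move along that trade-off. Nor does the protocol treat a pass as success: Protocol 9.1 plans no hypothesis tests, and Protocol 9.5 sizes the cohorts on posterior probability above the minimal ORR. A study-wide stop is compatible with a per-indication rule, because the IDMC's remit in Protocol 10.1.11 is wider and Protocol 4.4 lets the sponsor discontinue for any reason. Counts by cohort at the August 2023 analysis are results, which belong in the study report rather than the SAP.

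**Conclusion.** No change to the plan is needed. The boundaries follow exactly from the stated rule, and the benchmark phrase, which appears in Protocol 9.4 and the synopsis but not in SAP 11.0, is loose wording whose meaning the same section supplies. A statistician writing the report would describe a stopped cohort as one whose 80% CI excludes the minimal ORR, and would not present a pass as evidence of benefit. Leniency towards a cohort at benchmark (stopped 14.2% to 16.6% of the time) is a fair trade for a 2.1% to 4.1% risk of stopping one at the minimal ORR. With the futility analysis already done, adding these probabilities would alter no decision.

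The figures assume looks at exactly the stated N, a binomial count, and the printed ORRs taken as exact. The IDMC charter is not among the documents, so the absence of stopping probabilities is established only for the protocol and SAP.
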